## Study Objectives

Determine how patients in an out-patient surgical setting interpret non-noxious stimulation, specifically focusing on vibration.

Perception of cutaneous stimuli is critical in the diagnosis and treatment of many dermatological diseases. However, there is little understanding of how global sensations varies across populations.

Specific aim 1: Variable perception and interpretation of a non-noxious stimulus.

Hypothesis: Different patient populations will show subtle, if any, difference of non-noxious stimulation.

Rationale: Historically, there is evidence citing differences in perception of acute noxious stimuli across age, history of exposure to pain, and gender. Little information is available regarding non-noxious stimuli. In previous work from our group and validated by other researchers, patients are largely able to tolerate the non-noxious stimulation of vibration. Our aim here is to determine whether this tolerability and interpretation shows any difference across cohorts, specifically those in an outpatient surgical setting.

Specific aim 2: Variable perception and interpretation of a noxious stimulus following a non-noxious stimulus

Hypothesis: Different populations will show a significant difference in perception of noxious stimulation

Rationale: As previously cited, different cohorts of humans has a wide variety in how pain, both acute and chronic, is perceived. In this aim, we can identify how the noxious stimulus of an injection of anesthetic varies across populations in an out-patient surgical setting. Further, it is known that the application of vibration prior to needle injection significantly reduces the pain felt by the patient. This aim can determine how this change varies across different patient cohorts.

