### **Participants**

All adults (18+) presenting for MMS, surgical excision, and/or other cutaneous cancer removal surgery at Falk Dermatologic Surgery Clinic affiliated with the University of Pittsburgh Medical Center (UPMC) were eligible for inclusion. Subject enrollment occurred during a 90-day period from April to June 2018. Eligible subjects were informed of the study 24-72 hours before treatment via phone call.

Patients with expressed interest in the study were given more information on the day of study, including the risks and benefits of participating. Any subsequent questions were answered at this time. All participants were given a pre-procedural questionnaire and provided written informed consent. A follow-up phone call was conducted post-procedure.

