### **Participant Training**

Participants underwent a training session to answer trial questions (“What is your pain level?”) using the 11-point Numeric Rating Scale (NRS) as well as descriptive adjectives of sensation (“Can you describe the sensation you felt on your skin?”). The vibratory anesthetic device (VAD) was placed on a ‘training site’ approximately 5 cm away from their treatment site

in the OFF mode for 15s (Figure 1). Participants were then asked to describe the sensation they felt on their skin as well as the NRS pain level experienced. This process was repeated with the VAD in the ON mode.

During this time, patients who were unable to discern between the VAD ON and OFF modes, expressed NRS>0, could not communicate effectively, had a language barrier or were unable to follow instructions were excluded (Figure 2).

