## **Statistical Considerations**

Unpaired 2-tailed Student's t-test was used for univariate analysis of all variables for comparison of NRS means. A threshold for significance was set at  $p < 0.05$ . All values collected were analyzed to report mean values  $\pm$  standard error from the mean.

Multivariate linear regression analysis was used to compare categorical variables (age, sex, and treatment site). Multivariate analysis of the overall cohort identified  $p < 0.2$  for age, sex, and treatment site. All further subgroup analysis was performed using multivariate analysis with a threshold for significance set at  $p < 0.05$ . All statistical analyses were calculated by RK with Igor Pro (Wavemetrics, version 8) and STATA (StataCorp, version 13) software and confirmed with a consulting statistician ([name]).

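### Aim 1 predicts little or no difference between populations, but the plan holds only difference tests, so no result could support that hypothesis and p > 0.05 would not be evidence of similarity

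*Combined protocol and SAP*

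**What the plan says.** Under Study Objectives, the hypothesis for Specific aim 1 is that "Different patient populations will show subtle, if any, difference of non-noxious stimulation". The rationale beneath it is worded more openly: "Our aim here is to determine whether this tolerability and interpretation shows any difference across cohorts". Aim 2 predicts the opposite kind of result: "Different populations will show a significant difference in perception of noxious stimulation".

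Statistical Considerations makes no distinction between the two aims. The "t-test was used for univariate analysis of all variables for comparison of NRS means", and "A threshold for significance was set at" p < 0.05. Linear regression covers age, sex and site of treatment. A level of p < 0.2 is mentioned for the overall cohort, and then "All further subgroup analysis was performed using multivariate analysis with a threshold for significance set at" p < 0.05. Results are reported as means with standard errors.

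No target number of patients is given. Participants describes recruitment only by its time window: "Subject enrollment occurred during a 90-day period from April to June 2018". Participant Training removes several groups before the main assessment, among them "patients who were unable to discern between the VAD ON and OFF modes, expressed NRS>0".

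**The concern.** A hypothesis of little or no difference needs an analysis that can bound the difference. A difference test can contradict such a hypothesis when it is significant. It cannot support it when it is not, because a non-significant result arises both when cohorts are alike and when the data are too few or too variable to tell. Aim 2 predicts a difference, so the same tests suit it. For Aim 1 the plan lacks the three things that would give a null result a meaning: a definition of *subtle*, an interval for the between-cohort difference, and a sample size.

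At stake is the conclusion on whether cohorts defined by age, sex and treatment site perceive vibration alike. If no test reaches 0.05, the plan gives the reader no way to separate similarity from imprecision.

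**Working it through.** **Figure to reproduce.** None. The documents state no sample size, power, SD, cohort size or margin for Aim 1. The MCID and SCID under Outcome measures cannot serve as a margin. They are relative changes from initial to final NRS, not differences between cohorts, and the formula divides by the initial NRS, so it is undefined when that is 0.

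**Inputs.** From Statistical Considerations: two-sided test, significance level 0.05. Assumed, not from the documents: true difference d = 1 NRS point, two cohorts of equal size n, SD from 1 to 2.5 points.

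**Step 1: chance that the planned t-test misses a 1-point difference.** The test has 2n − 2 degrees of freedom and non-centrality d / (SD × √(2/n)). The miss rate is the probability that a non-central t with these values falls between −t(0.975) and +t(0.975). For SD 2 and n = 20, the non-centrality is 1 / (2 × √0.1) = 1.58 and the critical value with 38 degrees of freedom is 2.02, giving 66%.

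| Assumed SD | n = 20 | n = 30 | n = 50 |
|---|---|---|---|
| 1 | 13% | 3% | 0.1% |
| 1.5 | 46% | 28% | 9% |
| 2 | 66% | 52% | 30% |
| 2.5 | 77% | 67% | 49% |

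**Step 2: which rows are plausible.** Aim 1 concerns the pre-injection scores under vibration (0 s and 5 s in Outcome measures). Retained patients had just scored 0 in training with the same device, off and on, so their scores probably sit near 0 with a small spread. At SD 0.75 and n = 20 the miss rate is only 1.6%. The higher rows describe better a population in which the excluded patients are restored.

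**Step 3: what an equivalence claim would need.** Take a margin of ±1 point as an example, a true difference of 0, and a 90% interval that must lie wholly inside the margin (two one-sided tests at 0.05). The half-width is t(0.95) × SD × √(2/n).

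- At SD 2 the half-width is 1.07, 0.86 and 0.66 points for n = 20, 30 and 50. An interval narrower than the margin is not enough, because it must also be nearly centred. The chance of success is about 21% at n = 30 and 60% at n = 50.
- For 80% power the normal approximation gives n = 2 × (SD × (1.645 + 1.282) / margin)². At SD 2 this is 2 × (2 × 2.927)² = 68.5, so 69 per cohort, or about 70 with the t-distribution. At SD 1, 1.5 and 2.5 it is 18, 39 and 108.
- On floor-limited data the same margin is passed almost automatically: about 99% of the time at SD 0.75 and n = 20, and essentially always at SD 0.5.

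So a change of test alone is not sufficient. On the retained patients only, an equivalence result would largely reflect the exclusion.

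**The case against.** The strongest reply is that Aim 1 is not clearly an equivalence claim. Study Design and Methods calls the study descriptive, the rationale asks whether there is any difference, and the hypothesis itself leaves room for a small one. A difference test addresses the rationale's question. This stands in part: it makes a formal equivalence test optional and estimation an acceptable alternative. It does not close the gap, because the plan still states a hypothesis of little difference with a significance threshold, and a descriptive aim needs estimates of cohort differences with intervals, which are not planned.

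A reader might infer that the plan treats p > 0.05 as confirming Aim 1. The documents do not say so. They set thresholds for significance and are silent on how a non-significant result is read. The point is that such a result has no defined meaning, not that the plan has assigned it a wrong one.

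A reader might also infer that the high miss rates at SD 2 describe this study. They rest on an assumed SD that sits badly with the training exclusion, as step 2 shows.

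Two smaller replies have some force. Means with standard errors let a reader derive a rough unadjusted interval, using the square root of the sum of the squared standard errors, although not one adjusted for the other factors. And the sections on design, enrolment and statistics are in the past tense, so a margin added now may no longer be prespecified.

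**Conclusion.** The point holds in limited form. The mismatch between a hypothesis of little difference and an analysis made up only of difference tests can be read directly from the documents and needs no assumption. The same is true of the missing interval, definition of *subtle* and sample size.

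The practical size is uncertain. With a true 1-point difference and 20 to 50 patients per cohort, the chance of a non-significant result runs from 0.1% to 13% at SD 1 and from 30% to 66% at SD 2. The difference, SDs and cohort sizes are all assumed. The documents do not support saying that similarity will be concluded wrongly, or how often. They do support saying that p > 0.05 would not be evidence of similarity.

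The fault is separate from the training exclusion: restoring the excluded patients would not make the test able to show similarity, and changing the test would not undo the selection. This is a cheap improvement.

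**What to change.** For Aim 1, for each of age, sex and treatment site:

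1. Report the adjusted between-cohort difference in pre-injection NRS under vibration, with its confidence interval.
2. State that a non-significant result will not be taken as evidence of similarity.
3. Claim no meaningful difference only if the 90% interval lies within a margin that is stated and justified. Label the margin post hoc if it is set after data collection. Otherwise report the comparison as inconclusive.
4. Include the training-phase NRS of patients excluded for scoring above 0, where it was recorded, so that the result does not merely reflect the floor created by the exclusion.

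If no margin can be justified, label Aim 1 as estimation only and keep items 1, 2 and 4.

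The cost is some wording and a few lines of analysis on existing data, with no new patients. The downside is that some comparisons will be inconclusive: at SD 2 and a 1-point margin, about 70 patients per cohort are needed for 80% power when the true difference is 0.

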## **Study Design and Methods**

This is a DESCRIPTIVE, RANDOMIZED, partially blinded study.

### **Study design**

A randomized, partially-blinded, parallel-group clinical study of perception and interpretation of a non-noxious vibration stimulus compared to placebo (vibratory device in “off” mode) during syringe-mediated local cutaneous infiltration of anesthetic was performed. The protocol was approved by the University of Pittsburgh Institutional Review Board (PRO17110134) and conforms to the ethical guidelines of the Declaration of Helsinki.

### **Participants**

All adults (18+) presenting for MMS, surgical excision, and/or other cutaneous cancer removal surgery at Falk Dermatologic Surgery Clinic affiliated with the University of Pittsburgh Medical Center (UPMC) were eligible for inclusion. Subject enrollment occurred during a 90-day period from April to June 2018. Eligible subjects were informed of the study 24-72 hours before treatment via phone call.

Patients with expressed interest in the study were given more information on the day of study, including the risks and benefits of participating. Any subsequent questions were answered at this time. All participants were given a pre-procedural questionnaire and provided written informed consent. A follow-up phone call was conducted post-procedure.

### **Participant Training**

Participants underwent a training session to answer trial questions (“What is your pain level?”) using the 11-point Numeric Rating Scale (NRS) as well as descriptive adjectives of sensation (“Can you describe the sensation you felt on your skin?”). The vibratory anesthetic device (VAD) was placed on a ‘training site’ approximately 5 cm away from their treatment site

in the OFF mode for 15s (Figure 1). Participants were then asked to describe the sensation they felt on their skin as well as the NRS pain level experienced. This process was repeated with the VAD in the ON mode.

During this time, patients who were unable to discern between the VAD ON and OFF modes, expressed NRS>0, could not communicate effectively, had a language barrier or were unable to follow instructions were excluded (Figure 2).

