### **Outcome measures**

Subjects' pain was assessed using the validated 11-point NRS (0 = no pain, 10 = worst pain imaginable). Pain level was evaluated at multiple time-points; pre-anesthetic injection with stimulus (VAD ON/VAD OFF) at 0s and 5s; the timepoint of anesthetic injection at 15s (NRS) with stimulus (VAD ON/VAD OFF); and 5s post-infiltration with no stimulus present. Patients communicated their pain level verbally at the above timepoints.

Relative change in NRS was calculated with the below:

$$\text{Relative Change} = 100 * \frac{NRS_{Initial} - NRS_{Final}}{NRS_{Initial}}$$

From the findings of Olsen et al., MCID and SCID was defined as a relative change of 22-56% and  $\geq 57\%$ , respectively.

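### The training-session exclusions select patients on the response that Aim 1 studies, and no Aim 1 analysis covers the patients removed

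*Combined protocol and SAP*

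**What the plan says.** Study Objectives sets the Aim 1 question: "Our aim here is to determine whether this tolerability and interpretation shows any difference across cohorts", with reference to outpatient surgery patients. The hypothesis there is of little or no difference.

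Participant Training describes a 15-second exposure with the device OFF, after which participants were "asked to describe the sensation they felt on their skin as well as the NRS pain level experienced". Then: "This process was repeated with the VAD in the ON mode". The section excludes "patients who were unable to discern between the VAD ON and OFF modes, expressed NRS>0, could not communicate effectively", together with those who "had a language barrier or were unable to follow instructions were excluded (Figure 2"). It does not name the mode to which the NRS>0 criterion applies.

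Outcome measures lists the readings closest to Aim 1 as pain scores "pre-anesthetic injection with stimulus (VAD ON/VAD OFF) at 0s and 5s".

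Statistical Considerations gives t-tests on NRS means and a linear regression on age, sex and treatment site. It defines no analysis set and does not mention the excluded patients. It assigns no analysis to Aim 1 or to the sensation descriptions.

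**The concern.** Failing to feel the difference between ON and OFF is a perception response. Reporting pain while the device vibrates is a tolerability response. Both are what Aim 1 sets out to compare between cohorts, and both are grounds for removal before the study readings begin. If cohorts differ in either, part of that difference leaves with the excluded patients and is never analyzed.

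Aim 1 results then describe patients who detect the vibration and report no pain in training, whereas the aim is stated for outpatient surgical cohorts generally. Because the hypothesis expects little difference, a finding of similarity among patients who all passed the same response screen is weak support for it.

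**Working it through.** **Text comparison.** The plan states no sample size, effect size or number excluded, so it has no figure to reproduce.

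- *Aim 1 response:* perception and tolerability of vibration, by cohort (Study Objectives).
- *Screen:* ON/OFF discernment and NRS of 0 (Participant Training).
- *Consequence among kept patients:* discernment is 100% in each cohort, so the cohort difference is 100% − 100% = 0. The share with training NRS>0 is 0% in each cohort, so that difference is also 0. The first follows from the rule alone. The second takes NRS>0 to cover both modes, which is the plain reading because the exclusions are stated for the session as a whole.
- *Recovery in the analysis:* none named in Statistical Considerations.

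**Carry-over to the 0s and 5s scores (illustration only).** All rates, correlations and cut-points below are assumed. Let *p* be a cohort's probability of NRS>0 on one rating, *t* = Φ⁻¹(1 − *p*), and *r* the correlation between the latent normal scores behind the training rating and a repeat rating. Then

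P(repeat NRS>0 | training NRS=0) = 1 − Φ₂(*t*, *t*; *r*)/(1 − *p*).

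Example with *r* = 0.6:

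- *p* = 0.05: *t* = 1.645, Φ₂ = 0.9155, and 1 − 0.9155/0.95 = 3.63%.
- *p* = 0.20: *t* = 0.842, Φ₂ = 0.6992, and 1 − 0.6992/0.80 = 12.60%.
- The gap is 12.60 − 3.63 = 8.97 points, against a true 15.

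For mean NRS, the statistic the plan uses, take ten cut-points common to both cohorts, starting at the NRS>0 threshold, and let the cohorts differ by a mean shift. The kept mean is the sum over cut-points of P(repeat score above the cut-point | training score below the first).

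Equal repeatability, true rates 5% vs 20%:

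| *r* | NRS>0 among kept | Gap (true 15 points) | Mean gap, cut-points 0.25 SD apart (true 0.44) | Mean gap, 0.5 SD apart (true 0.26) |
|---|---|---|---|---|
| 0.3 | 4.51% vs 16.73% | 12.2 | 0.34 | 0.21 |
| 0.6 | 3.63% vs 12.60% | 9.0 | 0.22 | 0.14 |
| 0.8 | 2.66% vs 8.87% | 6.2 | 0.12 | 0.08 |

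Unequal repeatability:

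| True rates | *r* | Among kept | Effect on gap |
|---|---|---|---|
| 2% vs 5% | 0.8, 0.3 | 1.2% vs 4.5% | widens from 3.0 to 3.3 points |
| 15% vs 20% | 0.3, 0.8 | 12.8% vs 8.9% | reverses, from +5 to −3.9 points |
| 10% vs 10% | 0.3, 0.8 | 8.7% vs 4.9% | false gap of 3.9 points |

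With cut-points 0.25 SD apart, the mean-NRS gap goes from 0.070 to 0.078 in the first row and from +0.16 to −0.15 in the second.

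Low rates, 1% vs 3% with equal *r*: the true 2.0-point gap becomes 1.8, 1.5 and 1.1 points at *r* = 0.3, 0.6 and 0.8. The mean gap of about 0.04 falls to between 0.04 and 0.02.

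**The case against.** The strongest reply is that this is a choice of target population. Aim 1 is framed around a non-noxious stimulus, and screening out patients who feel pain or nothing keeps the stimulus perceptible and non-noxious for those studied. That purpose is sound for Aim 2, "Variable perception and interpretation of a noxious stimulus following a non-noxious stimulus". For Aim 1 it holds only in part, because the rationale also asks about tolerability, which a pain-free screen removes from view.

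Other points that stand as limits:

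- **Mode.** If NRS>0 referred to OFF alone, ON-mode training pain would not be fixed at 0. Discernment still would be.
- **Status of the items.** Training NRS and discernment are not listed outcomes. Their effect on the 0s and 5s scores depends on repeatability, which the documents do not give.
- **Size.** The plan reports that "patients are largely able to tolerate the non-noxious stimulation of vibration". If few score above 0, few are removed and the absolute effect is small, as the 1% vs 3% case shows.
- **Model.** It uses a single rating as the screen. The plan takes two, and each patient's later readings are in one randomized mode.
- **Descriptions.** Kept patients can still describe vibration differently, so this part of Aim 1 is only partly affected.
- **Figure 2.** It is cited beside the exclusions but was not in the copy reviewed, and may give counts. No claim is made that exclusion reporting is missing.

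Statistical Considerations also says that all collected values were analyzed. That sentence concerns reporting means with standard errors and names no Aim 1 comparison that includes the excluded patients.

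**Conclusion.** The concern holds and should be fixed. Confidence is high that the screen overlaps the Aim 1 response and that no stated analysis recovers what it removes.

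The direction and size of the effect on the 0s and 5s scores are not established. Attenuation is likely if repeatability is similar across cohorts. If it differs, gaps can shrink, widen or reverse. The figures above show what is possible under assumed inputs and do not estimate this trial's bias.

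The randomized ON/OFF comparison of injection pain is not biased by the screen if exclusions came before allocation; Participant Training does not state the order. On that condition, the effect on Aim 2 is limited to generalizability.

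**What to change.** Define the Aim 1 analysis set as everyone who had the training exposure, apart from the communication, language and instruction exclusions, which are ordinary feasibility criteria. Compare the following by age, sex and treatment site, with 95% confidence intervals:

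- NRS>0 with the device ON;
- NRS>0 with the device OFF, shown separately because pain in that mode is not intolerance of vibration;
- ON/OFF discernment;
- sensation descriptions, grouped into stated categories.

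State the mode to which the NRS>0 exclusion applied. Report exclusions by reason and cohort if Figure 2 does not already do so. Keep the restricted set for Aim 2.

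If the training responses were kept, the cost is analysis-set wording and a few tables. The plan says the responses were asked for but not that they were retained for excluded patients, and it describes enrollment as complete. If they were not retained, the cost is one scope sentence limiting the Aim 1 conclusion to patients who detect the vibration and report no pain in training.

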### **Intervention**

The VAD is a 10cm, handheld, battery-operated device by Finever. When ON, the device oscillates at a continuous frequency of 100Hz. It is non-experimental and available for purchase over-the-counter. The device was customized by positioning a cotton ball at the tip with subsequent placement into a nitrile glove.

The VAD, anesthetic injection and infiltration, and surgical procedure were all performed by a single, board-certified dermatologic surgeon ([name]). The anesthetic used in all cases was lidocaine hydrochloride 1% with epinephrine 1:100,000 and buffered with 8.4% bicarbonate 1:10 (Hospira Inc.). The anesthetic was prepared and administered in a 3 ml syringe with a 30-gauge needle. Anesthetic was prepared the day of the procedure.

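### Aim 2 compares perception of a noxious stimulus between non-randomised cohorts, but the amount and extent of the injection are not fixed, not reported as recorded and not modelled, so cohort differences in NRS may partly reflect stimulus size

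*Combined protocol and SAP*

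**What the plan says.** Under Study Objectives, the aim 2 hypothesis is "Different populations will show a significant difference in perception of noxious stimulation". The rationale says that "we can identify how the noxious stimulus of an injection of anesthetic varies across populations in an out-patient surgical setting" and, of the reduction in pain with vibration, that "This aim can determine how this change varies across different patient cohorts". Aim 2 thus contains two kinds of comparison: injection pain directly between cohorts, and the vibration effect between cohorts.

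On the stimulus, the Intervention section says "The anesthetic used in all cases was lidocaine hydrochloride 1% with epinephrine 1:100,000 and buffered with 8.4% bicarbonate 1:10" and "The anesthetic was prepared and administered in a 3 ml syringe with a 30-gauge needle". One surgeon handled the device, the injection and the operation. The Participants section admits patients "presenting for MMS, surgical excision, and/or other cutaneous cancer removal surgery".

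Under Outcome measures, two readings are taken at or after the noxious stimulus: one at the moment of injection (15 s) and one 5 s after infiltration, with the device no longer applied.

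Statistical Considerations provides unpaired t-tests for univariate comparisons and then states: "Multivariate linear regression analysis was used to compare categorical variables (age, sex, and treatment site". Procedure type, lesion size and amount injected do not appear in any described model.

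**The concern.** A difference in NRS between two groups can be read as a difference in perception only if both groups received a comparable stimulus, or if differences in the stimulus are adjusted for. Here the drug, needle, syringe size and operator are held constant. The amount and extent of infiltration are not. A syringe size is not a delivered volume.

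Randomisation does not help with this part of aim 2. It balances stimulus size between device ON and device OFF, but age, sex and treatment site are not assigned. If one cohort tended to have larger infiltrated fields, its scores could be higher with no difference in perception, and the plan as written would count that as support for its hypothesis. An imbalance in the other direction could hide a real difference. The plan provides no means of telling these cases apart.

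**Working it through.** **Figures in the plan.** The documents give no sample size, standard deviation, effect size or injected volume, so there is no figure to reproduce. The check is a comparison of sections, followed by an illustration on assumed inputs.

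**Sections side by side**

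- Fixed (Intervention): surgeon, buffered solution, syringe size, needle gauge.
- Not stated as fixed or recorded in any section: volume given, rate, number of needle entries, area infiltrated, lesion size.
- Pooled (Participants): Mohs surgery, excision and other skin-cancer removal.
- Modelled (Statistical Considerations): age, sex, treatment site. The univariate t-tests adjust for nothing.

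**Which comparisons are exposed**

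1. *Direct cohort differences.* Suppose NRS = perception + b × volume. The difference between cohorts A and B then contains b × (mean volume in A − mean volume in B). This term is zero only if b = 0 or the mean volumes are equal.
2. *ON minus OFF within a cohort.* Randomisation makes mean volume equal in the two arms in expectation, so b × volume cancels. Comparing this difference across cohorts is then also free of the additive term. It would be affected only if volume changed the vibration effect itself, if volume differed by arm, or if the percentage relative-change scale were used, where an additive shift need not cancel.
3. *Timing.* Anything injected after the 15 s reading cannot affect that reading. The reading 5 s after infiltration follows the whole infiltration and is the more exposed of the two.

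**Illustration (every input assumed).** No true difference in perception; SD 2 NRS points; two-sided alpha 0.05; b from 0 to 1 NRS point per ml; difference in mean volume from 0 to 1 ml. The bias is b × difference, so it runs from 0 to 1 × 1 = 1.0 NRS point. With n per cohort, SE = 2 × √(2/n), and by normal approximation

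rejection rate = Φ(bias/SE − 1.96) + Φ(−bias/SE − 1.96).

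Example: n = 50 gives SE = 2 × √0.04 = 0.40. A bias of 0.5 gives 0.5/0.40 = 1.25, and Φ(−0.71) + Φ(−3.21) ≈ 0.24.

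| Bias (NRS points) | n = 25 | n = 50 | n = 100 |
|---|---|---|---|
| 0 | 5% | 5% | 5% |
| 0.25 | 7.3% | 9.6% | 14.3% |
| 0.5 | 14.3% | 24.0% | 42.4% |
| 1.0 | 42.4% | 70.5% | 94.2% |

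The table shows what a given bias would do. It is not evidence that any bias exists. When the bias is not zero, a larger sample makes the false conclusion more likely.

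**The case against.** A reader might infer that volume and extent did vary with lesion and procedure, and hence that the cohort results do mix perception with stimulus size. The documents do not support that. Variation is a reasonable inference from the mixed procedures, but no section states it, and the sentence about the syringe describes something standardised. Confounding also needs stimulus size both to differ between cohorts and to affect the scored reading. The documents give no data on either. This objection stands, and the point is worded accordingly.

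A reader might also extend the problem to all of aim 2. That goes too far, because an additive effect cancels in expectation from the randomised contrast. This too stands.

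Three further objections stand in part. First, one surgeon, one solution and one needle gauge remove some variation, and treatment site may track more of it; neither accounts for procedure type or lesion size within a site. Second, the study is described as descriptive, and the rationale can be read as asking about pain from routine injection. On that reading the unadjusted comparison is legitimate, but the hypothesis itself speaks of perception. Third, enrolment is reported as completed between April and June 2018, so nothing can now be recorded prospectively, and nothing shows that needle entries were captured. This limits the remedy to existing records and to wording.

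**Conclusion.** The point holds in a limited form. Direct aim 2 comparisons by age, sex and site may partly reflect the size of the stimulus, because its amount and extent are not fixed, not reported as recorded and not modelled. The 5 s post-infiltration reading is the more exposed and the 15 s reading less so. The documents do not allow the size to be estimated. Under the assumed inputs it runs from nothing to 1.0 NRS point, and zero is a live possibility. The illustrative error rates rest on an assumed SD, slope, volume difference and cohort size, and should not be used to argue severity. The randomised ON versus OFF contrast on the NRS scale is not biased by an additive volume effect. What is not supported, as matters stand, is an unqualified conclusion that cohorts differ in perception.

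**What to change.** In Statistical Considerations:

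1. Add procedure type as a covariate in the direct aim 2 cohort comparisons by age, sex and site. It should be known for every patient, since it is the basis of eligibility. Add pre-operative lesion size where existing records hold it. Both precede randomisation, so adjusting for them is safe.
2. If injected volume is on record, tabulate it by cohort and by arm. The table by arm is a useful check because the surgeon who handled the device also gave the injection. Use volume only in a sensitivity analysis, because it arises after allocation.
3. Where these data are not available, report aim 2 as differences in reported pain from routine injection, not differences in perception, and state the limitation.

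None of this changes how anesthetic is given. The cost is a search of existing records, a few degrees of freedom and a narrower conclusion. Adjustment for procedure type and lesion size removes only the part of the variation in stimulus that goes with them, so some caution in wording remains appropriate even after step 1.
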